## 2.2. Background

Nonclinical in vivo and in vitro studies of psilocybin found via literature searches demonstrate that when administered orally to rats psilocybin is rapidly dephosphorylated to psilocin in the intestinal mucosa by alkaline phosphatase and a nonspecific esterase, with approximately 50% of the total volume of psilocin absorbed from the digestive tract (Kalberer 1962). Maximum plasma levels are achieved after approximately 90 minutes (Chen 2011). When administered systemically (i.e., bypassing the gut), initial psilocybin metabolism is performed by tissue phosphatases, with in vitro studies indicating the kidneys as being among the most active metabolic organs (Horita 1961). Across species tested, the highest levels of psilocin were found in the neocortex, hippocampus, and thalamus (Hopf 1974).

Recent clinical studies using pharmaceutical-grade oral psilocybin under controlled conditions have been performed in healthy volunteers and various subpopulations to characterize the safety profile and evaluate the biological response (Tryp-8802 IB). The clinical studies presented similar safety profiles, with both psychological and physical AEs reported. During dose sessions, the most common adverse psychological events included anxiety, negative emotional states and paranoid/delusional thinking, and the most common physical effects were increased BP and HR, mild nausea, and mild headache.

Preliminary efficacy of psilocybin in clinical studies showed an improvement in symptomatic response in indications including substance use disorder, treatment resistant depression, and anxiety. Overall, psilocybin has been well tolerated at the doses examined in the clinical studies.

A detailed description of the chemistry, pharmacology, efficacy, and safety of TRP-8802 is provided in the current Tryp-8802 IB.

#### 2.3. Benefit/Risk Assessment

Information about the known and expected benefits and risks and reasonably expected adverse events of TRP-8802 may be found in the Tryp-8802 IB.

Due to the psychoactive nature of TRP-8802, it should only be administered in a controlled setting per this clinical protocol. The safety of participants in this study will be enhanced by testing within a "set and setting" protocol as described by Lyons (2018) and by Johnson (2008). By addressing the set (the emotional/cognitive/behavioral state/mindset and expectations of study participants before TRP-8802 exposure) and setting (the physical environment in which the exposure occurs) of the experience, the risk of participants reporting an event which is distressing or injuring themselves can be reduced. Participants will be asked to discuss their session experience thoroughly with the goal of maximizing its therapeutic benefit.

CONFIDENTIAL 19 27 February, 2024

Hallucinogen-persisting perception disorder (HPPD) is a very rare but potentially serious disorder that may occur as a significant adverse effect with the use of psychedelic compounds (mainly lysergic acid diethylamide [LSD]). It is characterized by symptoms such as visual disturbances, derealization, and depersonalization that last from weeks to years after use (Espiard 2005). No cases of HPPD have been reported in volunteers given psilocybin in recent research studies (Griffiths 2016, Studerus 2012, Griffiths 2011). In studies involving cancer patients examining cancer-related anxiety and depression, no cases of HPPD were identified and no patients developed any symptoms of paranoia or anxiety that required pharmacological intervention or anything more than reassurance from session therapists (Studerus 2011).

The risk of experiencing HPPD with 2 doses of TRP-8802 is expected to be very low, and the risk of its occurrence will be reduced by screening participants for potential risk factors such as severe substance use disorder and by excluding people reporting HPPD or other significant adverse events after prior use of hallucinogens. As these symptoms can present even after the duration of the study, participants will be educated about HPPD. If the symptoms were to occur, participants will be instructed to inform the study team immediately (during the study period), and to seek medical care (after the study period), to rule out HPPD.

Higher doses of psilocybin (greater than 0.3 mg/kg) also may transiently lead to elevated mean BP, peaking 30 to 60 minutes following psilocybin administration and returning to baseline levels after 90 to 180 minutes without necessitating further interventions (Griffiths 2006; Hasler 2004). The severity of elevations in BP was usually asymptomatic and was graded as mild or moderate. Although several subjects in a University of Wisconsin dose-escalation study reached BP elevations that were graded as moderate, they remained asymptomatic (Brown 2017). It is not clear whether the changes in BP and HR are due to the elevated psilocin concentration directly or to the psychedelic effect caused by this active metabolite. Psilocybin appears to produce only slight sympathetic system activation (Hasler 2004; Gouzoulis-Mayfrank 1999).

Transient elevations of HR were common in subjects receiving psilocybin at doses of 0.3 mg/kg or more. The time course of these elevations in HR is similar to those seen for the elevation in BP, peaking between 60 to 120 minutes after the dose. This is similar to time of peak psilocin concentrations and peak psychedelic effect. Again, it is not clear whether or not the changes in BP and HR are directly due to the elevated psilocin concentration or caused indirectly by the psychedelic effect. In a phase 1 dose-escalation study in healthy volunteers, there were several instances in which mild bradycardia and tachycardia were noted. Psilocybin resulted in an increased HR, with slightly higher mean change from baseline in HR ( $\Delta$ HR) at higher psilocybin doses and corresponding higher psilocin exposures (Dahmane 2021). The maximum mean  $\Delta$ HR was observed at the time of psilocin maximum observed concentration (Cmax) (i.e., at 2 hours post dose) in nearly all psilocybin dose groups, and mean  $\Delta$ HR decreased with decreasing psilocin concentration at subsequent time points. Instances of bradycardia or tachycardia were unimodal, with no swing between bradycardia and tachycardia after a given dose. The episodes of bradycardia and tachycardia reported in recent studies were asymptomatic ("mild" or Grade 1) and did not require treatment (Tryp-8802 IB). Further information can be found in the current Tryp-8802 IB.

Mild headaches are common within the 24 hours after a dose of psilocybin. No auras or photo/phonophobia are associated with these headaches, which respond well to a single dose of

CONFIDENTIAL 20 27 February, 2024

acetaminophen. The headaches did not appear to be dose-related in one study, with no higher incidence after doses of 0.6 mg/kg versus 0.3 mg/kg (Brown 2017).

Taking into account the measures taken to minimize risk to participants in this study, the known and potential risks identified in association with TRP-8802 are justified by the anticipated benefits that may be afforded to participants with FM.

CONFIDENTIAL 21 27 February, 2024

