## 5. Study Population

Candidates who express an interest in participating in this study will undergo pre-screening. Prior to coming in for the screening visit, potential participants will be asked questions to see if they meet the inclusion/exclusion criteria. If they meet these criteria and are interested in participating, potential participants will provide informed consent electronically or will be invited to come in for the official screening visit, at which time obtaining informed consent will be completed.

Prospective approval of protocol deviations to recruitment and enrollment criteria, also known as protocol waivers or exemptions, will not be permitted.

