#### **Medical Conditions**

- 1. Participant has had (within the past 1 year) a cardiovascular condition such as coronary artery disease, stroke, angina, uncontrolled hypertension, a clinically significant ECG abnormality (e.g., atrial fibrillation), prolonged QTc interval (i.e., QTc > 450 msec), artificial heart valve, or transient ischemic attack.
- 2. Participant has epilepsy with a history of seizures.
- 3. Participant has insulin-dependent diabetes.

4. Participant is taking an oral hypoglycemic agent and has a history of hypoglycemia.

- 5. Participant has active auto-immune disease (e.g., lupus, rheumatoid arthritis).
- 6. Participants has any clinically significant lab abnormalities per a complete blood count and metabolic panel (e.g., elevated liver enzymes). Please see screening in section 4.1.1.
- 7. Participant has a current or past history of meeting Diagnostic and Statistical Manual of Mental Disorders, 5th edition (DSM-5) criteria for schizophrenia spectrum or other psychotic disorders (except substance/medication-induced or due to another medical condition), or bipolar I or II disorder measured via SCID-5 and SCID-5-PD.
- 8. Participant has a current or past history (within 1 year) of meeting DSM-5 criteria for a moderate or severe alcohol, tobacco, or other drug use disorder (excluding caffeine) measured via relevant questions from the SCID-5.
- 9. Participant has a history of a medically significant suicide attempt.

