#### **Prior/Concomitant Therapy**

- 10. Participant is taking psychoactive prescription medication (e.g., opioids, tramadol, benzodiazepines) on a regular basis (i.e., more than 2 times a week).
- 11. Participant is currently taking 300mg/day of bupropion or antidepressants other than selective serotonin reuptake inhibitors (SSRIs), selective norepinephrine reuptake inhibitors (SNRIs).
- 12. Participant is currently taking monoamine oxidase inhibitors (MAOIs) on a regular basis (daily or most days). For individuals who have intermittent or PRN use of such medications, TRP-8802 sessions will not be conducted until at least 5 half-lives of the agent have elapsed after the last dose.
- 13. Subjects taking prohibited medications. The list of prohibited medications should include antihypertensive medications, UGT1A9 or 1A10 inhibitors (e.g., regorafenib, rifampicin, phenytoin, eltrombopag, mefenamic acid, diflunisal, niflumic acid, sorafenib, isavuconazole, deferasiroxor, ginseng) and aldehyde or alcohol dehydrogenase inhibitor (e.g., disulfiram).
- 14. Participant is currently taking prohibited drugs of abuse, including methamphetamine, illicit opioids (e.g., heroin), cocaine, 3,4-Methylenedioxymethamphetamine (Ecstasy/Molly), or hallucinogens (e.g., mescaline or peyote).
- 15. Participant has any use of hallucinogens in the past 6 months or has had a total lifetime hallucinogen use of 10 or more times.
- 16. Participant tests positive for cocaine, methamphetamine, or opioids on urine drug testing.

CONFIDENTIAL 31 27 February, 2024

17. Participant has a psychiatric condition judged to be incompatible with establishment of rapport or safe exposure to TRP-8802.

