## e. Is a congenital anomaly/birth defect

#### f. Other situations:

- Medical or scientific judgment should be exercised by the investigator in deciding whether SAE reporting is appropriate in other situations such as significant medical events that may jeopardize the participant or may require medical or surgical intervention to prevent one of the other outcomes listed in the above definition. These events should usually be considered serious. Examples of such events include invasive or malignant cancers, intensive treatment for allergic bronchospasm, blood dyscrasias, convulsions or development of intervention dependency or intervention abuse.
- HPPD see Section 2.3 for definition.

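### Section 2.3 counts on excluding people with past HPPD or other significant reactions to hallucinogens, but no criterion in Section 5.2 states that exclusion

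*Combined protocol and SAP*

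**What the plan says.** Section 2.3 (Benefit/Risk Assessment) puts the HPPD risk after two doses as very low and names two measures that lower it further. One is screening for risk factors, with severe substance use disorder as the example. The other works "by excluding people reporting HPPD or other significant adverse events after prior use of hallucinogens". The section closes by judging the risks justified in light of the measures taken to limit them, so both measures belong to the benefit/risk argument.

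Eligibility is set out in Sections 5.1 (14 inclusion criteria) and 5.2 (23 exclusion criteria). The exclusions nearest to the promise are these:

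- Criterion 7 excludes a current or past "schizophrenia spectrum or other psychotic disorders (except substance/medication-induced or due to another medical condition), or bipolar I or II disorder measured via SCID-5 and SCID-5-PD".
- Criterion 8 excludes, currently or within 1 year, a "moderate or severe alcohol, tobacco, or other drug use disorder (excluding caffeine) measured via relevant questions from the SCID-5".
- Criterion 14 begins "Participant is currently taking prohibited drugs of abuse", and its list includes hallucinogens.
- Criterion 15 reads "Participant has any use of hallucinogens in the past 6 months or has had a total lifetime hallucinogen use of 10 or more times".
- Criterion 17 excludes a psychiatric condition that is judged to stand in the way of rapport or of safe exposure to the study drug.

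Elsewhere in the current text HPPD is treated as something that may happen on study. It is on the list that prompts Safety Review Committee review (Section 10.1.5). It also appears under the SAE definition in Section 10.2.2 ("HPPD see Section 2.3 for definition") and in the abbreviation list.

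**The concern.** A benefit/risk statement describes a protection that the operative eligibility text does not contain. Section 5.2 is what a site works through when it decides on a candidate, so a protection stated only in 2.3 may not be applied, or may be applied unevenly.

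The gap matters for three reasons. First, the people concerned are the ones the protocol itself singles out for protection. Second, safety is the primary endpoint in a study of about 10 participants, and HPPD counts as an SAE. Under Section 5.5, one SAE considered at least possibly related pauses dosing. Recurrent or worsening symptoms in someone with prior HPPD would be hard to attribute. Third, monitoring on study cannot fully replace selection at entry. Section 2.3 itself notes that symptoms can appear after the study is over, whereas Section 8.4.1 collects adverse events only from Baseline to the End of Therapy visit.

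**Working it through.** The plan gives no figure to reproduce and no formula applies. The check compares Section 2.3 with every place where its exclusion could be put into effect.

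**Step 1: split the promise.** Section 2.3 names (a) screening for risk factors such as severe substance use disorder, and (b) exclusion on the basis of a reported past reaction to a hallucinogen.

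**Step 2: look for (a).** Criterion 8 covers moderate or severe use disorder, current or within 1 year. Measure (a) has a counterpart.

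**Step 3: look for (b).**

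| Section 5.2 item | What triggers it | Does it reach a past reaction? |
|---|---|---|
| Criterion 7 | Psychotic or bipolar disorder, current or past | Not if the psychosis was substance-induced, which it exempts |
| Criterion 8 | Use disorder | No |
| Criterion 14 | Current use | No |
| Criterion 15 | Use within 6 months, or 10 or more lifetime uses | No; the reaction plays no part |
| Criterion 17 | Present psychiatric condition, by judgement | In part: current HPPD or another current psychiatric sequela, if so judged |
| The other 18 (23 − 5) | Unrelated matters | No |

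Count: 0 of 23 exclusion criteria state measure (b), and 1 of 23 (criterion 17) could apply it to some people at the site's discretion. None of the 14 inclusion criteria mentions a past reaction.

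**Step 4: look in the screening procedures.** Section 4.1.1 and the Schedule of Activities list medical history, SCID-5 and SCID-5-PD, but no named question about earlier reactions to hallucinogens. If one of these did bring a reaction to light, the only criterion that might apply is 17.

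**Step 5: test a candidate.** Take a person with 3 lifetime uses, the last 2 years ago, followed by perceptual symptoms that persisted and then resolved.

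- Criterion 15: 3 is below 10 and 2 years is longer than 6 months, so it is not met.
- Criteria 8 and 14: no use disorder and no current use, so neither is met.
- Criterion 7: no psychotic disorder, so it is not met. Had the episode been a substance-induced psychosis, the wording "other psychotic disorders (except substance/medication-induced or due to another medical condition" would take it outside this criterion.
- Criterion 17: it is worded for a condition the person has now, so it does not clearly reach a resolved one.

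This person is not expressly excluded by 5.2, yet belongs to the group that 2.3 says is excluded.

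**Step 6: size.** The group affected is the subset of candidates with 1 to 9 uses, all more than 6 months ago, who also had a significant reaction. The documents give no count, and 2.3 calls HPPD very rare. If one such participant among about 10 had an event, that would be 1/10 = 10 percentage points of the AE proportion described in Section 9.4.2. The shift would be zero if the same participant had any other AE, because that summary counts participants.

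**The case against.** The strongest reply is that the protection is not absent. Criterion 17 lets the site refuse someone with current HPPD. Medical history, the SCID interviews, the medical-stability criterion (inclusion 6), the physician's visit before first dosing (Section 4.1) and the interview before each session (Section 4.1.4) are further chances to notice a problem. The pre-screening questions mentioned in Section 5 are not reproduced, so sites may in fact ask about past reactions. Section 2.3 is itself protocol text that the site is bound to follow.

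This has force against saying that the safeguard has no effect, or that such a person would certainly be enrolled. It does not close the gap. None of these steps names a prior reaction, and criterion 17 depends on judgement and does not clearly reach resolved HPPD or a non-psychiatric reaction.

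A reader might also infer several stronger things that the documents do not support:

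- That the very low HPPD risk depends on the exclusion. Section 2.3 presents the exclusion as a further reduction, after reporting that recent psilocybin studies saw no cases.
- That everyone with 1 to 9 older uses is affected. Only those who also had a significant reaction are.
- That the bar on waivers forces enrolment. Section 5 says "Prospective approval of protocol deviations to recruitment and enrollment criteria, also known as protocol waivers or exemptions, will not be permitted", which stops a site from setting a criterion aside but does not oblige it to enrol everyone who passes.
- That criterion 7 flatly contradicts 2.3. Section 2.3 never names drug-induced psychosis, so the conflict rests on reading its phrase about other significant adverse events to include it. That is plausible, but it is an inference. The exemption also limits criterion 7 alone and makes nobody eligible. The HPPD gap stands without it.
- That an on-study event could not be told apart from pre-existing disease. Section 10.2.1 counts an exacerbation as an AE and a fluctuation without worsening as not. Attribution would be difficult, but there is a rule.

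**Conclusion.** The inconsistency is real and limited. Section 2.3 relies on an exclusion that no criterion in 5.2 states, and criterion 17 is a partial, discretionary backstop. The supportable conclusion is that candidates with 1 to 9 older uses and a past significant reaction are not expressly excluded and could be enrolled. Their number is unknown and may be small.

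This rests on the written criteria and procedures as they stand. It assumes that no unseen pre-screening form or manual supplies the missing question. If one does, practice may already match 2.3, but the eligibility section would still not say so. The documents do not show whether 2.3 or 5.2 reflects the intended rule, and this review does not choose between them.

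**What to change.** Reconcile Section 2.3 with Section 5.2, in particular criteria 7, 15 and 17. The sponsor and the investigator should decide which text carries the intent, and there are two consistent outcomes:

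- If the exclusion is intended, 5.2 should state what 2.3 already describes, and the screening interview should ask about it in anyone with earlier hallucinogen use. The exemption in criterion 7 should then be made consistent with that statement.
- If it is not intended, 2.3 should stop listing it as a risk-reduction measure, and the benefit/risk conclusion should be restated without it.

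Either way the text should make clear whether criterion 17 is meant to cover past as well as present reactions. The cost is a short amendment. The first outcome adds one screening question and may lose a few candidates, whom 2.3 already describes as excluded. No analysis or sample-size text needs to change.

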## 4.1. Overall Design

- All participants must have FM or have had FM symptoms for at least a year, and meet the 2016 FM Survey Criteria for FM. Exclusion criteria include certain co-morbid psychiatric disorders (e.g., psychotic disorders, bipolar I or II disorder, substance use disorder), history of a medically significant suicide attempt, and use of certain medications (e.g., anti-depressants).
- All participants enrolled in the study are expected to receive 2 doses of TRP-8802 separated by 2 weeks during in-center study intervention sessions.
- "Active intervention" includes baseline deep phenotyping, preparation, study drug administration, integration, and EOT deep phenotyping.
- Study visits may have visit "windows" as shown in the Schedule of Activities (SoA, Section 1.3)
- Further details regarding dosing and therapy sessions are provided in the Psychotherapy Manual.
- One of the physicians associated with the study will have a brief visit with the study participant during screening or prior to the first dosing session.
- The Lead Facilitator will be a doctoral level PhD/MD-level psychotherapist (or equivalent). Acceptable degrees for Lead Facilitators are: Clinical and Counseling Psychologists (PhD/PsyD), Physicians and Psychiatrists (MD or DO) or Masters of Social Work (MSW). The Co-Facilitator will have at least a bachelor's degree in mental health and at least one year of clinical experience in a licensed mental health care setting.
- The total duration of study participation for an individual participant is approximately 8 months, including screening, preparation, administration, integration, EOT, and follow-up.
- The total planned duration of the entire study is expected to be 18 months.
- There are no provisions for extending the study for any participants or for entry to rollover studies.
- An SRC will be responsible for the assessment of safety and to make recommendations with regard to study progression (Appendix 1, Section 10.1.5).

The timing and a description of these assessments are also provided in the SoA, Section 1.3 and in Section 8.

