# 5.5. Criteria for Temporarily Delaying Enrollment or Administration of Study Intervention

If any of the stopping rules below is met, dosing will pause until the SRC convenes (either routine or ad hoc) to review details of the event and/or additional data. If, after further review of the data, the SRC determines that no stopping rule has been met (e.g., AE determined to be unrelated to the study drug) or that if a stopping rule has been met there is a way to safely continue the trial (e.g., appropriate safety monitoring can be implemented), then dosing may resume. The occurrence of any of the following events will result in a temporary halt of dosing:

- one SAE considered at least possibly related to the study drug
- one Grade 3 or Grade 4 AE considered at least possibly related to the study drug
- clinically similar Grade 2 AEs considered at least possibly related to the study drug in 2 participants

CONFIDENTIAL 33 27 February, 2024

The study may be discontinued at any time by the Institutional Review Board (IRB), the FDA, or other government agencies as part of their duties to ensure that research participants are protected.

CONFIDENTIAL 34 27 February, 2024

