## 8.4.1. Time Period and Frequency for Collecting AE and SAE Information

All AEs and SAEs will be collected from the Baseline visit until the EOT visit, at the time points specified in the SoA (Section 1.3). Medical occurrences that begin before Baseline deep phenotyping but after obtaining informed consent will be recorded as Medical History, not as AEs.

All SAEs will be recorded and reported to the sponsor or designee immediately and under no circumstance should this exceed 24 hours, as indicated in Appendix 2, Section 10.2.3. The investigator will submit any updated SAE data to the sponsor within 24 hours of it being available.

Investigators are not obligated to actively seek information on AEs or SAEs after the conclusion of the study participation. However, if the investigator learns of any SAE, including a death, at any time after a participant has been discharged from the study, and he/she considers the event to be reasonably related to the study intervention or study participation, the investigator must promptly notify the sponsor.

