## 10.1.5. Safety Review Committees Structure

The SRC will be responsible for the assessment of safety and to make recommendations regarding study progression. The SRC will be composed of the principal investigator, a study therapist, and a study physician. Participant safety, which includes safety signal detection at any time during the study, will be continuously monitored by the SRC. All safety data collected will be summarized and reviewed by the SRC for agreement of next steps.

In particular, data will be reviewed by the SRC if one of the following Stopping Rules is met (Section 5.5):

- one SAE considered at least possibly related to the study drug
- one Grade 3 or Grade 4 AE considered at least possibly related to the study drug
- clinically similar Grade 2 AEs considered at least possibly related to the study drug in 2 participants
- HPPD

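### Section 2.3 does not ask participants to tell the study team about HPPD symptoms after the study period, so a late case could fail to reach the site (low priority)

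*Combined protocol and SAP*

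**What the plan says.** Section 2.3 (Benefit/Risk Assessment) singles out HPPD as a delayed harm: "As these symptoms can present even after the duration of the study, participants will be educated about HPPD". On what to do if symptoms occur, "participants will be instructed to inform the study team immediately (during the study period), and to seek medical care (after the study period"). The study period is not defined there or elsewhere.

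HPPD then appears in two operational places. The SAE definition in Section 10.2.2, under other situations, carries the line "HPPD see Section 2.3 for definition". Section 10.1.5 says that "data will be reviewed by the SRC if one of the following Stopping Rules is met", cites Section 5.5, and gives HPPD as the fourth item. Section 5.5 has only three items and does not name HPPD. Its first item is "one SAE considered at least possibly related to the study drug".

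Section 8.4.1 closes AE and SAE collection at the End of Therapy (EOT) visit and does not require the investigator to look for events once participation is over. It does require prompt notification of the sponsor "if the investigator learns of any SAE, including a death, at any time after a participant has been discharged from the study" and judges it reasonably related. Section 10.2.4 provides a paper route for a new SAE that a participant reports after the electronic tool is closed.

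On timing, Section 4.4 ends participation at Visit 15 (Day 204), and Section 4.1 states: "The total planned duration of the entire study is expected to be 18 months".

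**The concern.** The protocol has a receiving end for late SAE reports (Sections 8.4.1 and 10.2.4), and the duty in Section 8.4.1 has no closing date. The participant instruction in Section 2.3 does not feed it. It assigns one action to each period: contact the team in the first, seek care in the second. A participant who follows it to the letter after leaving the study has no prompt to contact the site.

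The stake is safety reporting on an event that the protocol itself treats as serious and as grounds for committee review. If participants enter one after another, some may still be awaiting a dose when an earlier participant has left. A case in that earlier participant would be relevant to the SRC only if the SRC hears of it.

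**Working it through.** **Inputs.** Screening starts at Day -42; Dose 1 is Day 22 and Dose 2 is Day 36; EOT is Day 64; Visit 15 is Day 204 (Section 1.3). Follow-ups fall 84 and 168 days after the final dose (Section 4.1.7). Individual duration is about 8 months and study duration 18 months (Section 4.1). A month is 30 days (Section 9.4.1). The target is about 10 completers (Section 9.2).

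**Reproducing the plan's figures.** Follow-up days: 36 + 84 = 120 and 36 + 168 = 204, as scheduled. Individual duration: 42 + 204 = 246 days, and 246 / 30 = 8.2 months, which agrees with about 8 months.

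**Longest gap between an exit and a later dose.** Assume that the first participant is screened on the first study day and the last completes at month 18.
- Study length: 18 x 30 = 540 days.
- Last participant's Dose 2: 540 - 168 = study day 372.
- First participant's Visit 15: study day 246.
- Gap: 372 - 246 = 126 days. To the last Dose 1, which is 36 - 22 = 14 days earlier, it is 112 days.

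With calendar months (18 x 365 / 12 = 547.5 days) the gap is 547.5 - 168 - 246 = 133.5 days.

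**Dependence on accrual.** If A is the number of days between the first and last entry, the gap is A - (204 - 36) = A - 168. The plan allows A up to 540 - 246 = 294, which returns 294 - 168 = 126. At A = 168 or less there is no gap. Accrual pace is not stated, so the table assumes 10 evenly spaced entries.

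| Accrual (days) | Participants dosed after the first exit | Dosing sessions after the first exit |
|---|---|---|
| 294 | 4 | 8 |
| 240 | 3 | 6 |
| 180 | 1 | 1 |
| 168 or less | 0 | 0 |

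At 294 days the spacing is 294 / 9 = 32.7 days. Four participants leave before the last Dose 2, by about 126, 93, 61 and 28 days, so the 126 days belongs to the first participant alone.

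**What cannot be computed.** The documents give no HPPD rate and no distribution of time to onset, so no probability of a missed case follows from them.

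**The case against.** Five points deserve weight.

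- **The term is undefined.** Section 4.1 separates individual participation from the whole study, and Section 4.4 defines the end of the study by the last participant. If the study period means the whole study, participants already report until everyone has finished. This stands as a caveat. The participant-level reading is the more natural one, because participation ends at Visit 15 and a participant has no obvious way of knowing when the last one finishes. The ambiguity itself is a reason to edit the sentence.
- **Passive routes exist.** A reader might infer that the instruction closes off late reporting, so that a late case would certainly go unreported. The documents do not support that. Advice to seek care does not forbid contacting the team, and Sections 8.4.1 and 10.2.4 both provide for late reports. What stands is that nothing in the protocol text prompts the participant to use them.
- **Participants may be told more elsewhere.** Consent material is not among the documents reviewed, so the point concerns the protocol wording only.
- **The primary endpoint is untouched.** A reader might infer that the primary safety result is compromised. Section 9.4.2 limits primary-endpoint AEs to Baseline through EOT (Day 64). A case first arising after Day 204 falls outside that analysis whether or not it is reported.
- **Late onset is not quantified.** The range of weeks to years in Section 2.3 describes how long symptoms last, not when they begin. The gap matters only for symptoms that arise or are recognised more than 168 days after Dose 2. Between Day 64 and Day 204 the instruction already sends participants to the team. Section 2.3 also calls HPPD very rare and the risk with two doses very low.

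**Conclusion.** The point holds as a low-priority improvement to safety reporting. The protocol treats HPPD as an SAE and an SRC trigger and accepts that it can appear after the study, but it does not ask participants to tell the team then. A late case could therefore fail to reach the site.

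The period in which this could matter for participants still being dosed runs from zero to about 126 days. The upper end assumes 30-day months, a full 42-day screening for the first participant, first screening at study start, last completion at month 18, and no use of visit windows. It is not an expected value. Outside that period the argument rests only on completeness of the SAE record. The finding also assumes that the study period means the participant's own participation.

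Separately, Section 10.1.5 cites Section 5.5 for a list that Section 5.5 does not match. A reader might infer from the omission that HPPD cannot pause dosing. That does not follow, because a case considered at least possibly related would meet the single-SAE item in Section 5.5. The lists still differ and must be reconciled. No sample size, error rate or efficacy analysis is affected.

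**What to change.** 1. Define the study period in Section 2.3.
2. In the same sentence and in the participant instructions, ask participants to report HPPD symptoms arising after their last visit to the study team as well as seeking medical care, at least until the last participant's final visit. The advice on medical care does not change.
3. State that such reports are handled as post-study SAEs under Sections 8.4.1 and 10.2.4.
4. Reconcile the lists in Sections 5.5 and 10.1.5, since only the latter names HPPD. Which list should stand is for the sponsor to decide.

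The cost is a short edit to the protocol and participant information, with no added visit or procedure. The downside is a few unsolicited reports to assess.
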